10.4.3 ANALYSIS OF THE SECONDARY ENDPOINT(S)

Secondary endpoints will include a composite outcome of symptomatic stone event, asymptomatic stone formation, or stone growth assessed at study conclusion. These outcomes will be analyzed using a logistic regression model, since asymptomatic stone formation or stone growth are subject to interval censoring (the exact occurrence time will be unknown).

24 hour urine total volume and lower urinary tract symptoms (as measured by CASUS) will be compared between intervention and control arms using t-test or Wilcoxon rank-sum test, based on the assumption of normality of the data.

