2 INTRODUCTION: BACKGROUND INFORMATION AND SCIENTIFIC RATIONALE

2.1 BACKGROUND INFORMATION

Urinary stone disease (USD) in the United States is an important medical, scientific, and public health problem. The prevalence of urinary stones has nearly doubled in the past 15 years¹ and health care utilization for treating patients with stones has risen in parallel.^{2,3} USD affects 1 in 11 persons in the United States, a prevalence similar to that of diabetes.¹ Estimates from the Urologic Diseases in America project suggest that aggregate expenditures for treating study participants with urinary stones exceeds \$10 billion, making USD one of the most expensive urologic conditions.²

Fluid intake is an appealing intervention for the secondary prevention of USD because it is effective, low risk, and inexpensive.⁴⁻⁷ In a randomized trial of adults with urinary stones, fluid intake that resulted in a urine output greater than 2L/day decreased stone recurrence by 55% and increased the time to recurrence by more than 1 year.⁴ Although stone formers are routinely counseled to drink more fluids, the average increase in 24-hour urine volume among adults with USD is only 300mL,⁸ suggesting that adherence to fluid intake recommendations is low even when the risks of non-compliance are severe. Identifying ways to change behaviors to decrease USD recurrence is an area in need of research.⁹

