3 OBJECTIVES AND PURPOSE

The primary aim of the study is to determine whether a multi-component program of behavioral interventions to increase fluid intake will result in reduced risk of stone disease progression over a 2-year period. Under this aim, the study will test the following specific hypotheses, comparing 1) intervention arm: individuals participating in a multi-component program of behavioral interventions targeting increased fluid intake (sufficient to achieve a urine output ≥ 2.5 L daily or ≥ 30 mL/kg/day for those study participants aged < 18 years and weighing < 75 kg); versus 2) control arm: individuals receiving usual care:

- a. **Primary hypothesis:** Participants in the intervention arm will have a reduced risk of symptomatic stones over 2 years.
- b. **Secondary hypothesis #1:** Participants in the intervention arm will have a reduced risk of stone disease progression (a composite outcome comprising symptomatic stone events, new asymptomatic stone on imaging, or stone growth of at least 2 mm on imaging) over 2 years.
- c. **Secondary hypothesis #2:** Participants in the intervention arm will have a reduced risk of forming new asymptomatic renal stones over 2 years.
- d. **Secondary hypothesis #3:** Fewer participants in the intervention arm will exhibit growth in existing renal stones of at least 2 mm on imaging over 2 years.
- e. **Secondary hypothesis #4:** Participants in the intervention arm will be more likely to achieve goal 24-hour urine output.
- f. **Secondary hypothesis #5:** Participants in the intervention arm will be more likely to develop lower urinary tract symptoms (LUTS).
- g. **Secondary hypothesis #6:** Greater urine output will be associated with reduced risk of stone disease progression, controlling for medication use (time updated), disease severity and clinical characteristics (e.g., body mass index).

h. **Secondary hypothesis #7:** Participants with pre-existing LUTS will be less likely to achieve 24-hour urine output goals as compared to those without pre-existing LUTS.

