Participants in the intervention arm will receive an individualized “fluid prescription”, which will be the additional volume of fluid intake needed to maintain a urine output of at least 2.5 L/day for study participants aged at least 18 years (adults) or 30 mL/kg/day for study participants aged 12-17 years inclusive (adolescents) and weighing < 75 kg; this additional fluid will be consumed from the smart water bottle. The prescription will be determined by the following equation: Initial Fluid Prescription = $1.2 \times (2.5L - \text{median urine volume on all 24-hour urine collections in the 12 months prior to enrollment})$. The fluid prescription may be modified, as needed, based on the 24-hour urine volume measurement obtained approximately 2 weeks after randomization. To reduce risk of unblinding treating providers, adjustments to the fluid prescription will be communicated by the study coordinator. The intervention arm also includes a behavioral program that consists of financial incentives and structured problem solving (SPS) to maintain the recommended fluid intake. The intervention period can be divided into phases of “induction,” “consolidation,” “taper,” and “maintenance.” The induction phase comprises the first 6 months of the intervention, and will initially include eligibility for FI on 100% of days. During induction, the intensity of the intervention can be increased for those study participants who do not consistently meet daily fluid intake goals by adding structured problem solving (SPS) to help participants develop feasible solutions to overcoming personal barriers to maintaining the prescribed fluid intake. The consolidation phase comprises the second 6 months and enables some additional potential for SPS-based adaptation of the intervention, but the frequency of the financial incentives will be slightly lower. The taper phase will comprise months 13 – 18, during which SPS is withdrawn and financial incentives are fully tapered. In the final 6-month maintenance phase, participants will have access only to “low touch” and low cost interventions (e.g., text reminders) that the participant selected to help sustain new habits of fluid consumption.

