4.2.2 SECONDARY ENDPOINTS

1. Asymptomatic formation of new stone detected by imaging
2. Increased size of existing stone by ≥ 2 mm in any dimension detected by imaging
3. Composite outcome: symptomatic stone recurrence, asymptomatic stone formation, increase of existing stone by ≥ 2 mm in any dimension detected by imaging
4. 24 hour urine total volume
5. Costs of study interventions and treatments for USD during the follow-up period
6. Presence of lower urinary tract symptoms (Comprehensive Assessment of Self-reported Urinary Symptoms)

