4.4 REQUIREMENT FOR LOW URINE VOLUME

Participants must have documented low urine volume to be eligible for the study. However, study investigators recognize that obtaining an accurate 24-hour urine volume poses challenges to efficient study recruitment given that participants will need to become oriented to the set-up and use of a smart water bottle.

We will accept for eligibility a 24-hour urine volume within the 12 months prior to the study visit. If more than one 24-hour urine specimen is available during that time period, then investigators will calculate the median volume of the available specimens; the median AND the most recent volume must be less than 2.0 L or 25 mL/kg if age < 18 and weight < 75 kg (adolescents ≥75 kg will follow the 2.0L urine volume threshold). Where possible, the investigators will also use conventional criteria (based on urine total creatinine) to assess if a urine specimen is an undercollection or overcollection. If no urine specimen during the 12 months prior to the day of screening is available, investigators will ask otherwise eligible participants to complete a 24-hour urine collection for volume, osmolality, and creatinine excretion.

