10.4.5 ADHERENCE AND RETENTION ANALYSES

24-hour urine total volumes will be the main adherence outcome.

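### Section 10.4.3 names no binary analysis for secondary hypotheses #4 and #5 or secondary endpoint 6, and its two-sample tests leave baseline urine volume and baseline CASUS unused

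*Combined protocol and SAP*

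**What the plan says.** Section 10.4.3 has two parts. Logistic regression is assigned to the stone outcomes (the composite, new asymptomatic stones, stone growth), with interval censoring as the reason. For the rest, "24 hour urine total volume and lower urinary tract symptoms (as measured by CASUS) will be compared between intervention and control arms using t-test" or a Wilcoxon rank-sum test, depending on normality. No covariate is named. Section 10.4.5 adds that "24-hour urine total volumes will be the main adherence outcome", without a method.

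The targets are set elsewhere:

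- Section 3, hypothesis #4: "Participants in the intervention arm will be more likely to achieve goal 24-hour urine output".
- Section 3, hypothesis #5: "Participants in the intervention arm will be more likely to develop lower urinary tract symptoms (LUTS").
- Section 4.2.2, endpoint 4: 24-hour urine total volume.
- Section 4.2.2, endpoint 6: "Presence of lower urinary tract symptoms (Comprehensive Assessment of Self-reported Urinary Symptoms").

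Goal attainment is not on the list in section 4.2.2. Section 10.2 repeats the 2.5 L goal among the other hypotheses of interest, and the protocol summary lists fluid intake adherence beside urine volume. Neither supplies a method.

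Baseline values exist. A 24-hour urine volume is an eligibility requirement (section 4.4) and a baseline descriptive (section 10.4.6). The schedule in section 7.3 marks a LUTS assessment at baseline, for adults, and again at months 6, 12, 18 and 24.

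Section 10.1 leaves the full description of methods to a separate SAP, which is not part of the document. Only the title of the CASUS appendix is present.

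**The concern.** Two things are at issue, and they differ in weight.

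The main one is a mismatch between question and analysis. Hypotheses #4 and #5 and endpoint 6 each ask what proportion of participants are in a given state. A t-test compares mean values and a rank-sum test compares distributions; neither yields a proportion, a risk difference or an odds ratio. As section 10 is written, the trial could report a volume difference without saying how many participants reached the goal that the intervention is built around. It could also report a CASUS score difference without saying how many adults developed the unwanted effect that hypothesis #5 predicts.

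The smaller one is efficiency. Both outcomes have a baseline measurement, and randomization is stratified by clinical center, age group and stone history, yet the named tests use none of this.

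**Working it through.** **Figures in the plan.** The protocol gives no SD, correlation, completion rate, LUTS rate or power for these outcomes, so there is no stated figure to reproduce. From section 10.5 I take 821 per arm. The 20% attrition there belongs to the time-to-event calculation; carrying it over to urine data (821 × 0.8 ≈ 656 per arm) is an assumption. The level is two-sided 0.05 (section 10.4.1), and I use 80% power.

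**1. Targets against methods in section 10**

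| Target | Type | Method named |
|---|---|---|
| Endpoint 4, urine volume | continuous | t-test or Wilcoxon: fits |
| Hypothesis #4, goal reached | yes/no | none |
| Hypothesis #5, LUTS develops | yes/no, new onset | none (CASUS by t-test or Wilcoxon) |
| Endpoint 6, LUTS present | yes/no | none (CASUS by t-test or Wilcoxon) |

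The logistic model cannot be read as covering the last three rows, because its stated reason concerns stone formation and growth. Section 10.4.4 does name a test of proportions for hyponatremia.

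**2. Does a mean difference determine goal attainment?** Assume normal volumes and take P(volume > 2.5 L) = 1 − Φ((2.5 − mean)/SD). Shift the mean by 0.3 L. That is the size in the background statement that "the average increase in 24-hour urine volume among adults with USD is only 300mL", used only as an illustration.

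| Control mean, SD (L) | Control | Shifted | Rise (points) |
|---|---|---|---|
| 1.6, 0.5 | 3.6% | 11.5% | 7.9 |
| 1.8, 0.7 | 15.9% | 28.4% | 12.5 |
| 2.0, 0.9 | 28.9% | 41.2% | 12.3 |
| 2.0, 0.5 | 15.9% | 34.5% | 18.6 |

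The same mean difference spans about 8 to 19 points. Conversely, equal means of 2.1 L with SDs of 0.5 and 0.8 L give 21.2% and 30.9% at goal, so the means can agree while the proportions differ by 9.7 points.

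**3. What a direct analysis of hypothesis #4 could detect.** Solve d = (1.960 + 0.842) × √[(p(1−p) + (p+d)(1−p−d))/n]. At 656 per arm, the detectable rise from an assumed control rate of 20%, 30% or 40% is 6.5, 7.3 or 7.7 points. At 492 per arm (60% completeness) it is 7.6, 8.4 or 8.8 points.

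**4. Hypothesis #5, adults free of LUTS at baseline.** Assume 80–95% adults, 40–80% of them free of LUTS, and 60–80% completeness:

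- low: 821 × 0.80 × 0.40 × 0.60 ≈ 157 per arm
- high: 821 × 0.95 × 0.80 × 0.80 ≈ 499 per arm

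From an assumed 20% control incidence, the detectable rise by the same formula is 13.9 or 7.5 points.

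**5. Precision from baseline adjustment.** Unadjusted detectable difference: (1.960 + 0.842) × √(2/656) = 0.155 SD. The entry cap below 2.0 L restricts baseline volume and so weakens its correlation with follow-up. Assume that the cap cuts at the median. The baseline variance is then multiplied by u² = 1 − 2/π = 0.363, and the restricted correlation is ρu/√(1 − ρ² + ρ²u²). Multiply 0.155 by √(1 − restricted ρ²):

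| Untruncated ρ | Restricted ρ | Variance cut | Detectable (SD) | Gain |
|---|---|---|---|---|
| 0.3 | 0.186 | 3.5% | 0.152 | 2% |
| 0.5 | 0.329 | 10.8% | 0.146 | 6% |
| 0.7 | 0.509 | 25.9% | 0.133 | 14% |

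At 492 to 738 per arm (60–90% completeness) the unadjusted figure is 0.179 to 0.146 SD, with the same relative gain.

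**The case against.** The strongest reply is that section 10.4.3 is a summary. Section 10.1 promises a separate SAP with the full methods, and hypotheses #6 and #7 have no method in section 10.4.3 either. That SAP, the Manual of Procedures or the CASUS appendix may already settle the models, the visit and the scoring. This stands as far as missing detail goes. The unnamed visit, the absent CASUS cut-off and the handling of month 24 assessments done early at discontinuation (section 5.4.2) cannot be called defects of the plan on this evidence. It does not remove the mismatch, because section 10.4.3 does name a method for LUTS, and that method does not answer the stated question.

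A second reply is that the volume test is valid and well powered. This also stands. At 656 per arm and SDs of 0.5 to 0.9 L, 0.155 SD is 0.08 to 0.14 L, and power for a 0.3 L difference exceeds 0.99. At mean 1.8 L and SD 0.7 L, the t-test detects about 0.11 L, while the test of goal attainment needs about 0.16 L. The binary analysis answers the stated question; it does not add power. The adjustment gain may also sit near its low end, since "We will accept for eligibility a 24-hour urine volume within the 12 months prior to the study visit", so some baselines will be old.

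A reader might infer that the unadjusted comparison is biased. Randomization protects it, so it is not. A reader might also infer that the repeated follow-up values would bring the detectable difference down to 0.08–0.10 SD. That holds only for an average over four visits, and the documents do not make such an average the target.

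**Conclusion.** The point holds in a limited form. As written, section 10 gives no analysis that estimates hypothesis #4, hypothesis #5 or endpoint 6, and section 4.2.2 omits goal attainment. This part rests on the text alone and on no assumed number. The unused baseline is a lesser matter: a 2% to 14% smaller detectable difference, on assumed correlations of 0.3 to 0.7, a cap at the median and 656 per arm.

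It would go too far to say that the trial will miss a LUTS effect because of the visit compared. The plan commits to no visit for that comparison, and the documents give no LUTS incidence or resolution rate from which to judge it.

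The stakes are limited, since these are secondary comparisons without multiplicity control (section 10.4.9). The change is still worth making because it is nearly free. Confidence is medium, because the separate SAP was not available.

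**What to change.** In section 10.4.3:

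- **Volume and CASUS score (adults):** compare the arms with a model adjusted for the baseline value and the randomization strata.
- **Hypothesis #4:** add logistic regression of attainment of the goal as the protocol defines it in section 3, adjusted for baseline volume and strata. List goal attainment in section 4.2.2.
- **Endpoint 6:** logistic regression of presence of LUTS in adults, adjusted for baseline LUTS and strata.
- **Hypothesis #5:** analyse new LUTS among adults without LUTS at baseline by a method that allows for unequal numbers of completed questionnaires. Suitable choices are a discrete-time or interval-censored model over months 6 to 24, or a repeated binary model. A plain logistic regression of LUTS at any visit should be avoided: the chance of being counted as a case would depend on how many questionnaires a person returned, and that may differ by arm.

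The visit, the CASUS cut-off and the visit windows should follow the separate SAP where it sets them; otherwise they should be fixed before unblinding. If the SAP already contains these analyses, it is enough to align section 10.4.3 with it.

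The cost is wording in section 10.4.3, one line in section 4.2.2 and routine programming. No data beyond those already scheduled are needed. A CASUS cut-off has to be agreed only if the appendix, Manual of Procedures and SAP contain none.

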10.4.4 SAFETY ANALYSES

Proportion of study participants developing symptomatic hyponatremia will be compared in the intervention and control arms using the Pearson's chi square test or Fisher's exact test, as appropriate.

10.4.5 ADHERENCE AND RETENTION ANALYSES

24-hour urine total volumes will be the main adherence outcome.

10.4.6 BASELINE DESCRIPTIVE STATISTICS

Baseline descriptive characteristics will include demographic (age, race/ethnicity, sex), socioeconomic status, body mass index, stone former status (first time vs recurrent), baseline medication use, and 24-hour urine volume at study entry. Baseline characteristics will be summarized as mean (standard deviation), median (25th, 75th percentiles), min and max.

10.4.7 PLANNED INTERIM ANALYSES

Interim efficacy analyses are not planned. However, the study leadership will monitor the data integrity and sample size assumptions while the study is ongoing at two time points: 1) when approximately 1/3 of the study participants are enrolled or 12 months after the 1st study participant enrolled, whichever occurs first; and 2) when about 2/3 of the study participants are enrolled or 20 months after the 1st study participant enrolled, whichever occurs first.

The event rate and dropout rate will be monitored in an aggregated fashion (ie, blinded to the intervention allocation). If the event rate is lower than anticipated, or if dropouts exceed the assumed

rate, then the target enrollment might be increased to maintain sufficient power to complete the study. In addition, if study enrollment is slower than expected, additional recruitment sites may be identified.

The fidelity of SPS will be assessed in two ways. First, health coaches and participants will complete separate checklists noting which elements of SPS were addressed during the session(s). Second, a 15% random sample of SPS sessions will be audio or video recorded and assessed by independent reviewers for adherence to the specified elements of SPS.

10.4.7.1 DATA AND SAFETY MONITORING REVIEW

A Data and Safety Monitoring Board (DSMB) will be appointed by the NIDDK to monitor study participant safety and to review performance of the protocol. A DSMB Charter that outlines the operating guidelines for the committee and the procedures for the interim evaluations of study data will be developed by the NIDDK and agreed upon at the initial meeting of the DSMB. Reports will be prepared regularly by the SDRC as requested by the DSMB chair. Depending upon the operational plan established by the DSMB, the report might include recruitment and retention rates, interim analyses, primary and secondary endpoints, SPS fidelity, adherence, and other information as requested by the committee. After each meeting, the DSMB will make recommendations to the NIDDK and the trial leadership about the continuation of the study.

10.4.8 ADDITIONAL SUB-GROUP ANALYSES

Subgroup analyses will be performed for the primary outcome among the ITT population in order to explore whether intervention on symptomatic kidney stone are consistent across subgroups. The same subgroup analyses will also be repeated in the per-protocol population. Subgroups of interest would be clinical centers, sex, race, age (adult/adolescent), baseline medical treatment for USD prevention and first time/recurrent stone former. An SPS treatment fidelity subgroup analysis may be conducted, if sufficient variability in fidelity exists. Subgroup analyses will be summarized in a forest plot which will include the interaction p-values.

10.4.9 MULTIPLE COMPARISON/MULTIPLICITY

A single primary outcome is specified, therefore no adjustment for multiple primary endpoint comparisons will be necessary. Secondary outcome comparisons will not be adjusted for multiple testing.

10.4.10 ECONOMIC ANALYSIS

In accordance with expert recommendations, the economic evaluation will be performed using the societal perspective.⁴⁶ Using data already being collected during the trial, the following economic model inputs will be estimated: (1) resources required to provide the study interventions; (2) patient time and (3) medical resource use. To estimate study intervention costs, we will use a tool specifically designed to estimate costs associated with patient-centered interventions (R01NR011873).⁴⁷ The costs of medical resource use will be assigned based on payment schedules (e.g., Medicare). To incorporate potential differences in health-related quality of life experienced by participants in the cost-effectiveness analysis,

health state utilities will be estimated from existing literature.⁴⁸ Full details of the economic analysis will be specified in the Economic Statistical Analysis Plan. Cost effectiveness analyses will use estimates of incremental cost effectiveness ratios (ICER).

[figure not shown]
10.5 SAMPLE SIZE

Conservative power calculations are based on symptomatic recurrence rates reported by Rule and colleagues.⁴⁹ The following assumptions are incorporated into the power calculation:

- 1) Unit of randomization: patient
- 2) Equal randomization ratio (1:1)
- 3) 15% event rate (composite of USD recurrence) over 2 years in control arm
- 4) 30% relative risk reduction for intervention arm (HR = 0.7)
- 5) 20% attrition rate (dropouts, loss to follow up)
- 6) Two-sided alpha of 0.05, log-rank test for time to event
- 7) 2 year follow up

$N = 821$ per arm (total = 1642 study participants) provides 80% power to detect the pre-specified relative risk. Sample size calculations were carried out using SAS (PROC POWER) version 9.4 (SAS Institute Inc., Cary, NC).

Study participants will be recruited from the 4 Clinical Centers over a 2-year period.

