4 STUDY DESIGN AND ENDPOINTS

4.1 DESCRIPTION OF THE STUDY DESIGN

This is a two arm randomized controlled trial that incorporates pragmatic features, an adaptable intervention, patient choice, and remote monitoring of fluid intake through a “smart” water bottle. The study period is 24 months and will enroll approximately 1642 participants. Randomization will be stratified within a clinical center by (adult vs. adolescent) and (first time vs. recurrent stone former). Intervention and control arm study participants will receive a smart water bottle that records daily fluid consumption, usual care including guideline-based recommendations of adequate fluid intake to decrease kidney stone recurrence, and periodic 24 hour urine collections.

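### 821 per arm does not give 80% power on the listed assumptions; with 24 months of follow-up and 20% attrition, power is about 63–69%

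*Combined protocol and SAP*

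**What the plan says.** Section 10.5 numbers its assumptions. The ones that drive the calculation are:

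- "Equal randomization ratio (1:1") allocation;
- "15% event rate (composite of USD recurrence) over 2 years in control arm";
- "30% relative risk reduction for intervention arm (HR = 0.7");
- "20% attrition rate (dropouts, loss to follow up");
- "Two-sided alpha of 0.05, log-rank test for time to event";
- two years of follow-up.

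It concludes that 821 "per arm (total = 1642 study participants) provides 80% power to detect the pre-specified relative risk". The software is named (PROC POWER in SAS), but the section gives no event target, no account of how attrition entered the calculation, and no accrual term in the numbered list. A 2-year recruitment period appears in a separate sentence after it.

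Follow-up is fixed for each participant. Section 4.1 says "The study period is 24 months and will enroll approximately 1642 participants". The Protocol Summary gives 24 months of participation and ends the study when the last participant completes that follow-up.

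Section 10.4.7 plans two blinded looks at the pooled event and dropout rates. If either is worse than assumed, "then the target enrollment might be increased to maintain sufficient power to complete the study".

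**The concern.** Every input needed to check the sample size is printed, and the stated power does not follow from them. This is the design claim for the trial's single primary endpoint, so it is the basis for enrolling 1642 people and for reading a non-significant result. If true power is in the sixties, a trial that runs exactly to plan has roughly a one-in-three chance of missing the effect it was built to detect.

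The monitoring rule inherits the problem. Rates that match the assumptions would be taken to mean that power is adequate, when those assumptions never gave 80%.

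**Working it through.** **Inputs (section 10.5, with fixed 24-month follow-up from section 4.1 and the Protocol Summary).** Control 2-year risk 0.15; hazard ratio (HR) 0.7; 1:1; two-sided alpha 0.05; 20% attrition; 821 per arm. Constant hazards are assumed, since the protocol gives no other shape.

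**Step 1: events needed (Schoenfeld).**
4 × (1.960 + 0.842)² / (ln 0.7)² = 246.8, so 247. Freedman's formula gives 253.

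**Step 2: risks.** The intervention 2-year risk at HR 0.7 is 1 − 0.85^0.7 = 0.1075. The two risks sum to 0.2575.

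**Step 3: try to reproduce 821.**
- No attrition: 246.8 / 0.2575 = 958 per arm.
- Inflated for 20% attrition: 958 / 0.8 = 1198 per arm.

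Neither is 821.

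**Step 4: events and power at 821 per arm.** Power is Φ(½ × √events × |ln 0.7| − 1.960).
- No attrition: 821 × 0.2575 = 211 events.
- 20% lost exponentially over 2 years. The control hazard is −ln(0.85)/2 = 0.0813 per year and the loss hazard is −ln(0.8)/2 = 0.1116 per year. The probability of an observed event is 0.1348 in control and 0.0966 in intervention, so 821 × 0.2314 = 190 events.
- 20% contribute nothing: 0.8 × 211 = 169 events.

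| Attrition at 821 per arm | Events | Power, Schoenfeld | Power, Lakatos | N per arm for 80% |
|---|---|---|---|---|
| None | 211 | 73.7% | 72.9% | 958–975 |
| 20% exponential | 190 | 69.1% | 68.3% | 1066–1085 |
| 20% no information | 169 | 64.0% | 63.3% | 1198–1218 |

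Simulated log-rank tests (4000 runs per setting) agree: about 74%, 68–69% and 63%.

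**Step 5: the other reading of the effect.** A literal 30% risk reduction is 15% against 10.5%, which is HR = ln(0.895)/ln(0.85) = 0.683. Power at 821 per arm is then 78–79% with no attrition, about 74–75% with exponential loss, and about 69–70% if 20% give no information.

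**Step 6: what 821 per arm can detect.** Solving for the HR that gives 80% power yields 0.663 with exponential loss and 0.646 if 20% give no information. These correspond to relative risk reductions of about 32% and 34%.

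**Step 7: where 821 may have come from (inference only).** Suppose 2 years of uniform accrual is added to 2 years of follow-up with a common closing date, so that participants are followed for 2 to 4 years. Then 664–673 per arm are needed, and dividing by 0.8 gives 830–842. Equivalently, 657 per arm (80% of 821) has 78–80% power in that setting. This is close to the stated number, but it counts events after month 24, which the design does not collect. A one-sided test with HR 0.683 comes about as near (833 per arm) and contradicts the stated two-sided test. The program inputs are not shown, so the origin cannot be settled, and the shortfall does not depend on it.

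**The case against.** Five points can be made for the plan.

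1. **The effect size is ambiguous.** On the literal risk-ratio reading, power with attrition is about 69–75%, so the span over both readings is about 63–75%. This is fair, but the protocol itself writes HR = 0.7, and neither reading reaches 80% with attrition. Even without attrition the literal reading stops at 78–79%.
2. **The 63–64% figure is a worst case.** Section 10.4.1 uses data up to the last collection, and section 5.4.1 continues assessments after withdrawal from the intervention. This stands: 63–64% is a lower bound, and 68–69% is closer to the planned analysis. Later dropout would raise power further, but not beyond the 73–74% obtained with none.
3. **The blinded review protects power.** It can raise enrolment, but only if events are fewer or dropouts more frequent than assumed. If both match the plan, nothing is triggered.
4. **Conservative may describe the 15% input.** Section 10.5 introduces the calculation with that word, and the cited source cannot be examined here. Whether 15% is cautious for this population is therefore open. The conclusion does not rest on it.
5. **The error does not bias the estimate or inflate type I error.** That is true. What is wrong is a stated operating characteristic of the design.

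**Conclusion.** The concern holds. On the listed inputs with 24 months of follow-up per participant, 821 per arm gives about 63–69% power at HR 0.7, which is 11–17 percentage points below the stated 80%. The type II error is about 31–37%. Removing attrition altogether still leaves power at 73–74%.

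The result assumes constant event hazards and takes the protocol's HR of 0.7 as the target. The position within the range depends on when dropouts leave, which the protocol does not specify. Schoenfeld, Lakatos and simulation agree to within about a percentage point. A true control risk above 15% would raise power, but that would be a different assumption from the one stated.

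**What to change.** In section 10.5:

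- Replace the 80% claim. With 821 per arm, 15% control risk, HR 0.7, 24-month follow-up and 20% attrition, power is about 63–69%, depending on the dropout model.
- State the dropout model and give the single power figure that follows from it.
- State the effect detectable with 80% power: HR about 0.65–0.66.
- Say whether the target is HR 0.7 or a risk of 10.5% against 15%, since the two differ.
- State 247 primary events as the information needed for 80% power at HR 0.7.
- If the word conservative is kept, tie it to the input it describes and not to the power calculation as a whole.
- If an input not listed (such as accrual time) produced 821, disclose it and reconcile it with the fixed 24 months.

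In section 10.4.7, compare the projected pooled event count with 247, and record that 169–190 events are expected at 821 per arm when all assumptions hold.

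**Cost.** The restatement changes wording only: no extra participants, procedures or analyses, and a less favourable stated power. Using 247 events as the benchmark will show a gap, so the sponsor should decide explicitly whether to accept the lower power or enlarge the trial. Reaching 80% at HR 0.7 would take 1066–1085 per arm with exponential loss (2132–2170 in total, 490–528 more than 1642). If 20% contribute nothing, it would take 1198–1218 per arm (2396–2436 in total, 754–794 more).
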